Between December 2006 and February 2008, Bakker and colleagues conducted a prospective randomised controlled trial on the use of compression stockings after endovenous laser ablation of the great saphenous vein¹⁰. One hundred and nine patients were approached with 93 finally randomised to use compression stockings for 2 days (Group A) and 7 days (Group B), respectively. All patients were followed up for 3 months post-treatment and the visual analogue scale (VAS) for pain was recorded at 48 hours, 1 week and 6 weeks. A physical examination and quality of life was assessed at 1 week and 6 weeks. Occlusion rate at the 3 month point was also evaluated. Physical function and vitality was shown to be significantly better in group B at 1 week follow-up, but there was no statistically significant difference at 6 weeks. At 1 week, it was also noted that the VAS score in group B (VAS score 2.0 ± 1.1) was significantly lower than in patients wearing compression stockings for 48 hours (VAS score 3.7 ± 2.1) ($p \leq 0.001$)¹⁰. No significant difference was, however, observed at 6 weeks post-procedure. Limitations of the study include the high drop out of the trial (40 out of the initial 109 approached) and the absence of any phlebectomies or sclerotherapy in the patients.

Elderman et al. carried out a randomised trial to assess the effect of compression stockings after endovenous laser therapy (EVLT) for great saphenous vein incompetence¹¹. Patients' reported pain scores and quality of life scores was evaluated on the day of the procedure, 2-3 days afterwards and 2-6 weeks post-procedure. A total of 111 patients were randomised to stockings (n=55) and no

stockings (n=56). There was a statistically significant difference in the pain scores in favour of the stockings group up to day 7, but this difference was no longer present by week 6. There was also a greater use of analgesia in patients in the no stockings group compared to patients wearing stockings ($p < 0.05$). In addition, patients wearing stockings reported a statistically significantly higher score of satisfaction at 2 days (4.44 vs 4.15) and at 6 weeks (4.59 vs 4.18). The absolute difference was, however, small. Two notable limitations of the study were the high level of drop outs (16 from each group) and the absence of any blinding.

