Patients randomised to group A will be asked to wear compression stockings for 1 week.

Patients randomised to group B and undergoing endothermal ablation only will not be provided with any compression. However, if they receive adjuvant treatment to their tributaries, they will be provided with bandages to wear for 24 hours only, with no further compression afterwards.

At baseline, patients will be asked to fill quality of life questionnaires (EQ-5D, AVVQ and CIVIQ) and will have their clinical scores assessed (CEAP and VCSS). On discharge after their varicose vein intervention, they will then be provided with a diary to record their post-procedural pain every day for 10 days using a validated visual analogue scale (VAS) as well as to record when they return to their normal activities and are back to work. They will also be asked to attend a follow-up in 2 weeks and at 6 months.

Patients' GP will also be sent a letter to inform them of their patient's participation in the study.

Follow-up

Patients will be followed up in the outpatient clinic at 2 weeks and 6 months.

Follow-up at 2 Weeks

At the 2 weeks' follow-up, the diary containing details of the pain scores and how soon patients were able to return to normal activities/work will be collected. In addition, patients will be asked about any bruising or phlebitis they have had in the two weeks after their procedure and how compliant they have been with the compression. They will be examined and the Venous Clinical Severity Score (VCSS) will be recorded. They will also be asked to fill in the EQ-5D, AVVQ and CIVIQ scores.

Follow-up at 6 Months

At the 6 months follow-up, patients will be examined and their VCSS will be recorded. They will also be asked to fill the EQ-5D, AVVQ and the CIVIQ scores. They will have a venous Duplex scan to determine occlusion of the treated vein.

Sample Size and Study Duration

We estimated the sample size needed to observe a difference of at least 10mm in the VAS score, with a standard deviation of 20mm. With power at 90% and 5% significance equivalence, we would need to recruit 174 patients (87 per group).

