Previous studies looking at compression stockings have shown drop out rates close to 37% at 3 months¹⁰. Therefore, if we estimate a drop out rate of about 50% by 6 months, we would need to recruit at least 348 patients. If we recruit at least 7 patients per week, this will be approximately a total of 364 patients that could potentially be randomised over the year. With 6 months follow-up, therefore, the study will be running for 18 months with a target recruitment of 350 patients.

Settings

Two hospital trusts in London will be recruiting patients for the study. These will be the:

1. Imperial College NHS Trust
2. North West London Hospitals NHS Trust

ETHICAL ARRANGEMENTS

Ethical approval will be sought from a Regional Research Ethics Committee as per the National Research Ethics Service. Patients will be screened by [name] (or another research fellow), who is also members of the direct care team, and patients thought eligible will be provided with information material about the trial and varicose veins and its treatments.

They will be invited to attend for their varicose vein procedures another day and will have until then to consider their participation into the trial (more than 24 hours to consider).

On the day of their procedure, they will be asked by [name] (or another research fellow) to confirm their consent by providing a written consent prior to participating in the trial.

The National Health Service (NHS) Trust Research and Development approval will also be sought prior to starting the trial.

DATA HANDLING & DISSEMINATION OF RESULTS

All patient data will be anonymised and stored on a password protected access database under the guidelines of the Data Protection Act 1998. Patient records will be kept on paper in the form of the diary card questionnaires and clinical scoring sheets. These will be kept in a locked filing cabinet at the and stored at the Charing Cross Hospital for 10 years in accordance with the Imperial College Trust Policy.

Data and study findings will be presented locally within the hospital, as well as national and international peer reviewed presentations and peer-reviewed journals.

Criteria for Electively Stopping the Trial or Other Research Prematurely

The trial may be stopped prematurely due to loss of equipoise or any major adverse effect as a result of treatment in any of the treatment arms.

Adverse events

No significant adverse events are expected.

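### The protocol states no masking for the VCSS or 6-month duplex assessor, and at 2 weeks it lists arm-revealing steps ahead of the VCSS examination

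*Combined protocol and SAP*

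**What the plan says.** **Blinding.** The only mention in the text is in the Background, which names "the absence of any blinding", alongside dropout, as a limitation of a cited randomised trial of stockings after laser ablation.

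**Two weeks.** Follow-up at 2 Weeks first lists collection of the diary. It then has patients asked about bruising and phlebitis and "how compliant they have been with the compression". After that comes the examination: "They will be examined and the Venous Clinical Severity Score (VCSS) will be recorded". The diary (Appendix 9) has a column for the day on which stockings were stopped, to be completed only by patients who were given them.

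**Six months.** "At the 6 months follow-up, patients will be examined and their VCSS will be recorded". For occlusion: "They will have a venous Duplex scan to determine occlusion of the treated vein". Neither sentence names the assessor or says what that person knows about the allocation.

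**Intervention.** "Patients randomised to group A will be asked to wear compression stockings for 1 week". Group B receives no stockings, and bandages for 24 hours only if tributaries were treated.

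**Staff.** Under Ethical Arrangements, screening and consent are done by a named fellow ("or another research fellow), who is also members of the direct care team"). Staffing of the follow-up clinics and of the duplex scans is not described.

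**Status of the outcomes.** Clinical change on the VCSS and occlusion at 6 months are secondary objectives. The primary objective is the patient's own VAS pain score over 10 days.

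**The concern.** Patients cannot be masked to whether they wear stockings, but the people who score the VCSS and read the duplex can be. Several VCSS rows (Appendix 6) require a graded judgement on examination. An assessor who knows the arm and holds a view on compression can shift those grades in one direction. A larger sample does not remove such a shift. It only makes the shift more likely to reach significance.

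The protocol contains no safeguard against this. At 2 weeks its listed sequence would give the assessor the allocation before the examination begins. At 6 months nothing prevents the treating or consenting clinician from doing the scoring with the allocation in view. A reader of the results could not tell whether a difference in VCSS or occlusion came from masked or open assessment.

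**Working it through.** **1. Where the arm becomes known, and whether it could be withheld**

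| Assessment | What could reveal the arm | Could it be withheld? |
|---|---|---|
| VCSS, 2 weeks | Diary column on stockings; compliance question; the scale's compression row; the patient; the assessor's own role in treatment or consent | Partly, by order of steps and choice of assessor |
| VCSS, 6 months | Compression row; the patient; the notes; the assessor's own role | Largely, if the form omits the arm and the compression row comes last |
| Duplex, 6 months | The scan request; the patient; the operator's own role | Most readily: reading occlusion needs no information on compression |

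Stockings are assigned for 1 week. Taking 6 months as about 26 weeks, they should have been off for about 26 − 1 = 25 weeks by the final visit, so they should leave no visible cue.

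**2. How far VCSS masking can reach**

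Appendix 6 has ten rows.
- Six are graded mainly by examination: varicose veins, pigmentation, inflammation, induration, ulcer number and ulcer diameter.
- Three rest wholly or partly on history: pain, timing of oedema and ulcer duration.
- One, compression, asks about stocking use itself.

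Masking can protect the first six. It cannot fully protect the other four, because the patient supplies the information.

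**3. The plan's own sample size, for reference**

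Inputs from Sample Size and Study Duration: difference 10 mm, SD 20 mm, power 90%, significance 5%.
- Normal approximation, two-sided: n = 2 × (1.960 + 1.282)² × 20² / 10² = 84.06, so 85 per group. The t-test needs 86. The plan states 87, which is reproduced within rounding.
- Dropout: 174 / (1 − 0.50) = 348, as stated.

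Masking changes none of these figures. At the planned 50% loss, 350 recruits leave 350 × 0.5 = 175 in total at 6 months, or about 87 per group.

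**4. Illustration of what a shift would do**

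The documents give no VCSS variance, no expected occlusion rate and no estimate of assessor bias, so the shift d (in SD units) is an assumption. With no true effect, the two-sided 5% t-test at n = 87 per group has 172 degrees of freedom, critical value 1.974 and non-centrality d × √(n/2) = d × √43.5 = 6.595d.

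| Assumed shift d | Non-centrality | Chance of a false significant difference |
|---|---|---|
| 0 | 0 | 5.0% |
| 0.10 | 0.660 | 10.1% |
| 0.20 | 1.319 | 25.9% |
| 0.30 | 1.979 | 50.3% |

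The calculation treats the shift as acting on the whole VCSS score. No corresponding figure can be given for duplex occlusion.

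**The case against.** The strongest reply is that the point concerns secondary outcomes only. The primary VAS is completed by the patient at home, and no assessor touches it. That stands, and it limits the weight of the point.

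Other parts of the reply also stand:
- **Silence is not a declaration.** A reader might infer that the plan intends open assessment. It does not say so, and the trial flowchart (Appendix 11) is not shown. Equally, the order in which the 2-week steps are listed is not a mandated sequence. What can be said is that no masking is stated and that following the text as listed exposes the arm.
- **The cited-trial criticism is not a direct contradiction.** As the Background describes it, that trial measured pain, quality of life, analgesia use and satisfaction, with no VCSS or duplex outcome. The remark shows awareness of the problem. It is not a standard that this protocol then breaks for its assessors.
- **Independent staff cannot be assumed.** A reader might take the mention of another research fellow as proof that an independent assessor is available. That phrase covers screening and consent only, and the study has no funder. Any request for a different assessor must depend on the rota.
- **Bruising and phlebitis at 2 weeks are asked of the patient.** Assessor masking would not protect them.
- **The percentages are not an estimate for this trial.** They follow from an assumed shift.

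The reply fails on one matter. Leaving the arm off a duplex request or a scoring form, and changing the order of steps within a visit, needs no extra person.

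**Conclusion.** The point holds as an omission with a cheap remedy. The protocol states no masking for the VCSS at either visit or for the 6-month duplex, and at 2 weeks it lists two arm-revealing steps before the examination. Two secondary outcomes are exposed. The primary VAS, the sample size and the 2-week bruising and phlebitis reports are not.

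The size of any bias is unknown. The 10% to 50% false-positive range rests on an assumed shift of 0.1 to 0.3 SD, no true effect, and 87 per group analysed.

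Masking is most feasible for duplex occlusion. For the VCSS it will be incomplete, because pain and other history-based rows rely on the patient and one row records compression. That masking can work at 6 months is an inference from the 1-week wearing period, and it depends on patients not disclosing their arm.

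**What to change.** Add a short passage to the follow-up sections, stating that:

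1. The allocation is not shown on the 6-month duplex request or VCSS form.
2. Where the existing rota allows, the 6-month assessor is someone who did not treat, consent or randomise that patient.
3. Patients are asked not to disclose their arm to the assessor.
4. At 2 weeks, the VCSS examination rows are scored before the diary is collected and compliance is asked.
5. The VCSS compression row is completed last, at 2 weeks and at 6 months.
6. One field on the form records whether the assessor knew the arm. Where masking was not possible, the assessment is reported as open.

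**Cost:** protocol wording, one form field and some scheduling effort. No treatment, visit, procedure or sample size changes, and items 1 and 3 to 6 need no additional assessor. The remaining weakness is incomplete masking of the VCSS, which the form field would at least make visible.

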There is currently uncertainty about the use of compression stockings following treatment of varicose veins. In their consensus statement in 2008, the International Union of Phlebology (IUP) stated that there is good evidence for using compression in certain clinical indications⁶. These include the management of telangiectasia after sclerotherapy, varicose veins in pregnancy, prevention of thromboembolism and healing of ulcers. However, a few questions remain unanswered, such as the length of treatment and level of compression to be used⁶. The Society for Vascular Surgery and the American Venous Forum recommend using compression stockings post-operatively for 1 week to prevent haematoma formation, pain and swelling⁷. The 2013 NICE Guidelines on Varicose Veins in the Legs recommended the use of compression hosiery for no more than 7 days after interventional treatment for varicose veins⁸. However, due to current uncertainty of compression bandaging or hosiery compared to no compression after interventional treatment for varicose veins, the NICE Guideline Development Group have advocated further research to evaluate the clinical and cost effectiveness of this post-procedure intervention⁸. The guidelines also suggested looking into the length of time compression bandaging should be worn if it shown to be beneficial⁸.

Several researchers have looked into the practice of using compression after venous ablation. In a survey of the management of varicose veins by the members of the Vascular Society of Great Britain and Ireland, Edwards et al. found that the majority of surgeons used bandages post-operatively, with 49% using elastic bandages⁹. The literature on the use of compression stockings following treatment of varicose vein is limited.

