Hamel-Desnos et al. undertook a randomised controlled trial looking at the effect of compression in patients receiving foam sclerotherapy of the saphenous vein¹². They noted that patients with compression had similar pain and quality of life scores to patients not wearing any compression. They concluded that additional use of compression had no impact on the effectiveness of obliteration of veins, satisfaction scores, symptoms and quality of life, and that further controlled trials were needed to answer the question of whether using compression results in any difference to the outcome of varicose vein procedures.

We, therefore, propose to undertake a multicentre randomised study looking at the effect of compression therapy after endovenous thermal ablation.

Description

This will be a multicentre randomised clinical trial looking at the impact of wearing or not wearing compression stocking following endothermal ablation (either endovenous laser treatment (EVLT) or radiofrequency ablation (RFA)) of incompetent truncal veins. **If clinically indicated, patients will receive adjuvant treatment (e.g., concurrent phlebectomies or foam injection).**

Patients will be randomised **to** group A (compression) and group B (no compression). Only the use of compression will be randomised while the decision as to which treatment to use will be at the discretion of the clinical team.

Target Population

Patients referred for treatment of symptomatic varicose veins will be recruited if they are found to have primary great saphenous (GSV) or small saphenous vein (SSV) incompetence on colour duplex scan.

Inclusion Criteria

- Adults over 18 years of age
- Symptomatic GSV or SSV vein reflux **>** 0.5 seconds on colour Duplex
- **Recurrent varicose veins (if suitable for endothermal treatment)**

Exclusion Criteria

- Current DVT

- Arterial disease (ABPI<0.8)
- Vein diameter < 3mm
- Patient who are unwilling to participate
- Inability or unwillingness to complete questionnaires

Intervention

Patients will be randomised to have compression (group A) or no compression (group B). The compression therapy used will be Class II compression stockings. The treatment offered will be endothermal ablation (either endovenous laser treatment (EVLT) or radiofrequency ablation (RFA)) of incompetent truncal veins. Adjuvant treatment to tributaries (e.g., concurrent phlebectomy or foam sclerotherapy) will be carried out, if indicated.

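### Active venous ulceration (CEAP C6) is not an exclusion, so a patient with an open venous ulcer can be allocated to the no-compression arm

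*Combined protocol and SAP*

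**What the plan says.** **Eligibility.** The Exclusion Criteria have five items: current DVT, ABPI below 0.8, vein diameter below 3 mm, unwillingness to take part, and inability or unwillingness to complete questionnaires. The Inclusion Criteria ask for an adult with symptomatic GSV or SSV reflux longer than 0.5 seconds and admit recurrent disease. Neither list mentions ulceration or CEAP class.

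**Treatment.** Under Intervention, "Patients randomised to group A will be asked to wear compression stockings for 1 week". For the other arm, "Patients randomised to group B and undergoing endothermal ablation only will not be provided with any compression". If Group B patients have adjuvant treatment to tributaries, "they will be provided with bandages to wear for 24 hours only, with no further compression afterwards".

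**Background.** The protocol reports a consensus statement that found "good evidence for using compression in certain clinical indications". The indications it then lists end with "prevention of thromboembolism and healing of ulcers". It adds that length of treatment and level of compression remain open.

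**Safeguard.** The Consent section lets the clinician, once a participant has entered, give a different treatment at any time if that is in the participant's interest. The reasons are recorded, and the participant stays in follow-up and analysis.

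**Data already collected.** CEAP and VCSS are scored at baseline. Appendix 7 defines class 6 as active ulcers, and Appendix 6 has rows for the number, duration and diameter of active ulcers.

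**The concern.** The trial is justified by uncertainty about compression after varicose vein treatment. An open venous ulcer is a separate reason to compress, and the Background reports good evidence for it without disputing that. The argument for equipoise is therefore not made for a C6 patient, yet the eligibility rules admit one. If that patient is allocated to Group B and the protocol is followed as written, a treatment that the protocol itself accepts is withheld. At stake is the care of those individual patients, not the trial's main result.

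**Working it through.** The plan gives no figure on this point, so there is none to reproduce. The check is a reading of the eligibility, treatment and consent text together, plus one subtraction.

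1. **Can a C6 patient enter?** Take an adult with symptomatic GSV reflux longer than 0.5 s, a vein of at least 3 mm, ABPI of at least 0.8, no current DVT, a purely venous open ulcer, and willingness to take part and complete the forms. Every inclusion criterion is met and no exclusion applies. The ABPI rule removes ulcers with marked arterial disease but not a purely venous one. The Target Population section refers to symptomatic varicose veins and does not restrict this to uncomplicated disease.

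2. **Can that patient reach Group B?** Yes. The sample size section plans equal groups (87 and 87), and no rule ties allocation to clinical class.

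3. **What does Group B provide?** The difference in planned compression from Group A is:
   - ablation only: 7 − 0 = 7 days;
   - ablation with tributary treatment: 7 − 1 = 6 days (bandages in place of stockings for the first day).

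   This is the difference between arms. It does not measure what an ulcer needs.

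4. **Does the protocol treat that difference as open for an ulcer?** The Background leaves open how long and how strongly to compress. It does not leave open whether compression helps ulcers heal.

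5. **Does anything before randomisation stop the allocation?** Under Ethical Arrangements, screening is done by a research fellow in the direct care team, and "patients thought eligible will be provided with information material about the trial". No criterion tells the screener that an open ulcer makes a patient ineligible. Baseline CEAP and VCSS carry no eligibility rule. The Consent clause operates only after entry.

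6. **How many patients?** The documents give no count or share of C6 patients, and none is assumed here.

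**The case against.** The strongest reply is that the Consent clause already deals with this. It applies at any stage after entry, so the clinician can compress the patient from the moment of allocation, and no period without compression is required. The screener is part of the direct care team and would probably notice an ulcer. This is real mitigation, and it is why the point is small. It does not close the gap: the clause is discretionary, it does not prevent the allocation, and it relies on departing from the protocol in a situation that can be foreseen at screening.

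Three further replies stand in part.

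- *Frequency and harm are unknown.* Correct. There may be no such patients, and the documents do not size the effect of a week without compression on an ulcer.
- *The clinical premise is one Background sentence about ulcer healing in general, not about the week after ablation.* Also correct, and it limits how strongly the point can be put. The same sentence lists other indications; no claim is made about those here.
- *Group B patients are only not given compression, so they could keep their own.* This is arguable after ablation alone. The wording for tributary treatment points the other way, and the protocol gives no instruction for a patient already compressed for an ulcer.

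A reader might infer that C6 patients in Group B will go without compression and be harmed. The documents do not support that, given the Consent clause and the missing count.

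A reader might also infer that overridden patients threaten the primary comparison. They do not. Suppose one Group B patient is compressed and gains the full 10 mm effect. The expected difference becomes 10 × (1 − 1/87) = 9.89 mm with 87 analysed per group, or 10 × (1 − 1/175) = 9.94 mm with 175. With SD 20 mm and a two-sided 5% t-test (sidedness is assumed; the plan does not state it), power moves from 0.907 to 0.900, or from 0.997 to 0.996. Keeping such patients in the analysis preserves the randomised comparison and is not a fault.

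**Conclusion.** The point holds as a minor patient-safety gap in the eligibility rule. Followed as written, the protocol lets a patient with an active venous ulcer be randomised to an arm that gives no compression, or 24 hours of bandages, while its own Background accepts compression for ulcer healing. The size is 6 to 7 fewer days of planned compression per C6 patient allocated to Group B, unless the clinician intervenes. The number of patients and the harm per patient cannot be given from the documents.

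The conclusion rests on two readings: that the exclusion list is complete as printed, and that the Background statement on ulcers is the protocol's own position, since it is reported without dispute. It is a change the sponsor could reasonably make. It does not call the design or the primary analysis into question.

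**What to change.** Add one line to the Exclusion Criteria: *active venous ulceration (CEAP C6)*. Identify it by routine clinical examination at screening, which needs no trial form. Confirm it from the baseline CEAP class after written consent and before randomisation. The order matters: screening comes before written consent, which is taken on the procedure day, so trial CEAP and VCSS scores should not be moved forward to the screening step.

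The cost is one line in a protocol amendment and an instruction that CEAP is scored before randomisation. No new data are collected. The downside is that a few screened patients may be lost and the conclusions will not extend to C6 patients.

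If the sponsor prefers the wider population, the alternative is one sentence under Intervention stating that compression for an active ulcer continues in Group B. That keeps these patients, at the price of a planned exception to the no-compression arm.

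### DVT and PE are not a named outcome, and apart from a general instruction to record adverse events nothing ascertains them or compares them between the arms

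*Combined protocol and SAP*

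**What the plan says.** **Rationale.** The Background reports that an international consensus "stated that there is good evidence for using compression in certain clinical indications", and its list of these includes "varicose veins in pregnancy, prevention of thromboembolism and healing of ulcers". The same paragraph opens by calling the use of stockings after varicose vein treatment uncertain.

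**Arms.** Under Intervention, "Patients randomised to group B and undergoing endothermal ablation only will not be provided with any compression". Group B patients who have adjuvant tributary treatment get bandages for 24 hours and nothing after that. Group A wears stockings for a week.

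**Outcomes.** The objectives cover pain, quality of life, VCSS, bruising and phlebitis, compliance, return to work and activities, occlusion and cost effectiveness. Neither DVT nor PE is among them.

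**Follow-up.** At 2 weeks, "patients will be asked about any bruising or phlebitis they have had in the two weeks after their procedure"; compliance, an examination, VCSS and the questionnaires complete the visit. At 6 months there is another examination with VCSS and questionnaires, and then: "They will have a venous Duplex scan to determine occlusion of the treated vein".

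**Where DVT does appear.** A current DVT is an exclusion criterion, and the clinical assessment sheet (Appendix 4) has a past-history tick item for DVT/PE. Both concern the patient's status before treatment.

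**Adverse events.** The Adverse events section states: "No significant adverse events are expected". Reporting Procedures then requires every adverse event to be recorded and sets out SAE reporting. Neither section names an event of interest, says how events are elicited, or provides for a table by arm.

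**Attrition.** The sample size section reads: "Therefore, if we estimate a drop out rate of about 50% by 6 months".

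**The concern.** The protocol screens for thromboembolic disease at entry but does not follow it up afterwards in any structured way, in a trial whose randomised difference is compression. If pain and cost favour group B, readers will take the result as support for leaving compression out and will ask how many clots occurred in each arm. As planned, the report could give only whatever reached the adverse event log.

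A count obtained that way has two weaknesses. It may be incomplete, especially after week 2, when the protocol describes no scheduled contact before 6 months and expects heavy loss by then. It may also be unequal: no blinding is described and patients know whether they are wearing stockings, so the readiness to mention a symptom, or to ask about one, could differ by arm. Neither weakness can be put right once follow-up has ended.

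**Working it through.** **Step 1: does any planned procedure look for DVT or PE?**

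| Place in the protocol | Content | DVT/PE ascertained? |
|---|---|---|
| Primary and secondary objectives | Pain, quality of life, VCSS, bruising, phlebitis, compliance, return to activity, occlusion, cost | No |
| Follow-up at 2 Weeks | Diary, bruising, phlebitis, compliance, examination, VCSS, questionnaires | Not as a listed item; no scan |
| Follow-up at 6 Months | Examination, VCSS, questionnaires, duplex for occlusion | Not as a listed item |
| AVVQ, CIVIQ-14, VCSS, EQ-5D, diaries (appendices) | Pain, swelling, skin changes, function | Symptoms only, no event |
| Reporting Procedures | Record all adverse events; SAE form | Passive; no method, no by-arm analysis |
| Criteria for stopping the trial | Any major adverse effect in an arm | Generic; no count specified |

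The SAE route is narrow. Under the listed criteria, a DVT managed without admission need not be an SAE, and reports to the ethics committee are limited to events judged both related and unexpected. The flowchart (Appendix 11) is not shown and could not be checked.

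**Step 2: the plan's own numbers.** Inputs from the sample size section: difference 10 mm, SD 20 mm, power 90%, 5% significance, drop-out 50%, target 350.

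- Two-sided comparison of means: n = 2(1.960 + 1.282)² × 20²/10² = 84.1, so 85 per arm or 170 in total, within 3% of the stated 174.
- Equivalence by two one-sided tests at 5%, true difference 0: n = 2(1.645 + 1.645)² × 20²/10² = 86.6, so 87 per arm, exactly the stated figure.
- Drop-out: 174/(1 − 0.5) = 348, as stated.
- Per arm at the target: 350/2 = 175. Half of that is about 87, the plan's own number per group.

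These figures were set for pain. They matter here only because they fix how many patients could be assessed for DVT/PE.

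**Step 3: what zero events would exclude.** The one-sided 95% upper limit with no events in n patients is 1 − 0.05^(1/n).

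- n = 175: 1 − 0.05^(1/175) = 1.70%.
- n = 87: 1 − 0.05^(1/87) = 3.38%.

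The second figure applies only to a 6-month assessment with half the arm present. The protocol gives no drop-out figure for 2 weeks.

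**Step 4: could the trial compare the arms?** The documents state no DVT/PE rate, so the rates below are assumptions: 0.5%, 1% and 2% with compression, doubled without it, two-sided 5%. With p̄ the mean of the two rates and δ their difference,

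power = Φ{[δ√n − 1.96√(2p̄(1 − p̄))] / √(p₁(1 − p₁) + p₂(1 − p₂))}.

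| Assumed rates | Power, 175 per arm | Power, 87 per arm | n per arm for 80% power |
|---|---|---|---|
| 0.5% v 1% | 8% | 6% | 4673 |
| 1% v 2% | 12% | 8% | 2319 |
| 2% v 4% | 19% | 12% | 1141 |

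At the assumed compression-arm rates, 175 patients would yield about 0.9, 1.8 and 3.5 events (0.005, 0.01 and 0.02 × 175). The normal approximation is rough at such counts, but the order of magnitude is clear.

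**The case against.** **The rationale is not contradicted.** A reader might infer that the protocol cites good evidence that compression prevents thromboembolism and then withholds it from half the patients. The text does not say that. The consensus statement covers general indications, alongside pregnancy and ulcers. The Background treats compression after varicose vein treatment as an open question, and the post-operative reasons it cites from a guideline are haematoma, pain and swelling. Some group B patients also receive short bandaging. This objection stands.

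**There is a safety net.** Every adverse event is to be recorded, attenders are examined at both visits, the AVVQ asks about leg pain and ankle swelling, local investigators report SAEs, and GPs know of participation. It would therefore be wrong to say that events have no route into the trial, or that capture is shown to be spontaneous only; the documents are silent on elicitation. Nor do they say that a patient who misses the 6-month visit is counted as free of events. What remains is that none of these routes is uniform, directed at DVT/PE or tied to a comparison by arm.

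**The gain is small.** No safety or non-inferiority claim is planned, and Step 4 shows that the trial could not support one. That is correct, and it limits the point to descriptive reporting. It does not remove it: an evenly collected count with an interval is more useful than an uneven one without.

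**The 3.4% limit mixes time points.** Drop-out by 6 months says nothing about attendance at 2 weeks, and patients lost later still contribute their 2-week answer. This stands, which is why the figure is given only for the 6-month assessment.

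**Conclusion.** The point holds as a gap in ascertainment and reporting. DVT and PE are not a named outcome, no listed visit item or scan is directed at them, and no comparison by arm is planned. General adverse event recording may pick up some events, but the protocol gives no means of knowing that it does so completely or equally.

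The size can be stated only as precision. With no events, the upper limit is 1.7% in a fully assessed arm of 175 and 3.4% if 87 are assessed at 6 months. Under assumed rates of 0.5% to 2%, a doubling would be detected with about 6% to 19% power. The conclusion rests on 1:1 allocation (implied by 87 per group), on the protocol's own 50% drop-out estimate, and on the flowchart containing nothing that changes Step 1.

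A reader might go further and infer that the trial is unsafe, or that the added data would let it declare omission of compression safe. The documents support neither inference. The pain analysis is unaffected; this is a cheap improvement whose data cannot be recovered later.

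**What to change.** 1. Name symptomatic DVT or PE, from procedure to 6 months, as a secondary safety outcome.
2. Add one direct question to the existing 2-week and 6-month visits (event, date, how confirmed), worded and asked identically in both arms.
3. In the GP letter that is already sent, ask for notification of such events up to 6 months. The letter's text is not in the documents; if it already asks for this, no change is needed.
4. Report counts and the risk difference by arm with exact confidence intervals, showing how many patients were assessed at each time point. Do not treat non-attenders as free of events.
5. State in advance that the comparison is descriptive and that the trial cannot show omission of compression to be safe with respect to thromboembolism.

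The cost is one question on two forms, one sentence in a letter and one table, through a small amendment with no extra visit or scan. Visits become slightly longer, and the report will carry an upper limit that will not be reassuring at this sample size.
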